Available pharmacokinetic results in subjects with melanoma, NSCLC, and other solid tumor types support a lack of meaningful difference in pharmacokinetic exposures obtained at a given dose among tumor types. Population PK analysis has been performed and has confirmed the expectation that intrinsic factors do not affect exposure to pembrolizumab to a clinically meaningful extent. Taken together, these data support the use of lower doses (with similar exposure to 2 mg/kg Q3W) in all solid tumor indications. The dose of 2 mg/kg Q3W is being evaluated in NSCLC in PN001, Cohort F30 and PN010, and 200 mg Q3W is being evaluated in head and neck cancer in PN012, which are expected to provide additional data supporting the dose selection.

Selection of 200 mg as the appropriate dose for a switch to fixed dosing is based on simulation results indicating that 200 mg will provide exposures that are reasonably consistent with those obtained with 2 mg/kg dose and importantly will maintain individual patient exposures within the exposure range established in melanoma as associated with maximal clinical response. A population PK model, which characterized the influence of

body weight and other patient covariates on exposure, has been developed using available data from 476 subjects from PN001. The distribution of exposures from the 200 mg fixed dose are predicted to considerably overlap those obtained with the 2 mg/kg dose, with some tendency for individual values to range slightly higher with the 200 mg fixed dose. The slight increase in PK variability predicted for the fixed dose relative to weight-based dosing is not expected to be clinically important given that the range of individual exposures is well contained within the range of exposures shown in the melanoma studies of 2 and 10 mg/kg to provide similar efficacy and safety. The population PK evaluation revealed that there was no significant impact of tumor burden on exposure. In addition, exposure was similar between the NSCLC and melanoma indications. Therefore, there are no anticipated changes in exposure between different tumor types and indication settings.

To ensure the safety and efficacy, the first 3 subjects will be dosed at 100 mg rather than 200 mg every 3 weeks. If the first 3 patients do not have any significant safety or efficacy issues the dose will be escalated to 200 mg every 3 weeks.

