5.2 Trial Treatments

The treatments to be used in this trial are outlined below in **Table 2**.

Table 2: Trial Treatment

Drug	Dose/Potency	Dose Frequency	Route of Administration	Regimen/Treatment Period	Use
MK-3475 ^{a, b}	100 mg	Every 21 days	IV infusion	6 cycles	Experimental
MK-3475 ^b	200 mg	Every 21 days	IV infusion	6 cycles	Experimental
BCG	1 vial	Every 7 days	Bladder Instillation	6 cycles	Approved

^aThe first 3 subjects will be dosed at 100 mg. If the Data Safety Review Team approves, the dose will be escalated to 200 mg with the fourth subject enrolled.

^bThe MK-3475 dosing interval may be increased due to toxicity as described in Section 5.2.3.3. BCG treatment may be interrupted or delayed as per the instructions for use supplied with BCG (Section 5.2.1.1.3).

BCG: One vial of BCG suspended in 50 ml preservative-free saline. BCG is to be given through a urinary catheter (intravesically) into the bladder. BCG treatment will occur once per week for 6 weeks. BCG treatment will commence on the 3rd cycle of treatment with MK-3475, Week 7. BCG is a FDA approved treatment and will be supplied commercially through the study site pharmacy.

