5.2.2 MK-3475 Treatment

5.2.3 Dose Selection/Modification

5.2.3.1 Dose Selection

The rationale for selection of doses to be used in this trial is provided in Section 4.0 - Background and Rationale.

A fixed dose of 100 mg MK-3475 will be given on Day 1 +/-3 days of a 21 day cycle for up to 6 cycles for the first 3 subjects. If one subject of the three requires the dose of MK-3475 to be withheld or discontinued, the 100 mg cohort will be expanded to 6 subjects. If two out of three or two out of six subjects develops toxicity that requires the dose to be withheld or discontinued, the dose will not be escalated to 200 mg MK-3475 every 3 weeks. All remaining subjects will be treated at 100 mg MK-3475 every 3 weeks for 6 cycles.

The Data Safety Review Team will make a determination if dose escalation to 200 mg is possible. The Data Safety Review Team automatically meets after 3 subjects have been enrolled and treated; however, a meeting may be called sooner, if deemed necessary.

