5.2.3.3 Dose Modification (Escalation/Titration/Other)

Adverse events (both non-serious and serious) associated with pembrolizumab exposure may represent an immunologic etiology. These adverse events may occur shortly after the first dose or several months after the last dose of treatment. Pembrolizumab must be withheld for drug-related toxicities and severe or life-threatening AEs as per Table 3 below. See Section 5.4.1 for supportive care guidelines, including use of corticosteroids.

Table 3

Dose Modification Guidelines for Drug-Related Adverse Events

Toxicity	Hold Treatment For Grade	Timing for Restarting Treatment	Treatment Discontinuation
Diarrhea/Colitis	2-3	Toxicity resolves to Grade 0-1	Toxicity does not resolve within 12 weeks of last dose or inability to reduce corticosteroid to 10 mg or less of prednisone or equivalent per day within 12 weeks
	4	Permanently discontinue	Permanently discontinue
AST, ALT, or Increased Bilirubin	2	Toxicity resolves to Grade 0-1	Toxicity does not resolve within 12 weeks of last dose
	3-4	Permanently discontinue (see exception below) ^a	Permanently discontinue
Type 1 diabetes mellitus (if new onset) or Hyperglycemia	T1DM or 3-4	Hold pembrolizumab for new onset Type 1 diabetes mellitus or Grade 3-4 hyperglycemia associated with evidence of beta cell failure	Resume pembrolizumab when patients are clinically and metabolically stable
Hypophysitis	2-4	Toxicity resolves to Grade 0-1. Therapy with pembrolizumab can be continued while endocrine replacement therapy is instituted	Toxicity does not resolve within 12 weeks of last dose or inability to reduce corticosteroid to 10 mg or less of prednisone or equivalent per day within 12 weeks
Hyperthyroidism	3	Toxicity resolves to Grade 0-1	Toxicity does not resolve within 12 weeks of last dose or inability to reduce corticosteroid to 10 mg or less of prednisone or equivalent per day within 12 weeks
	4	Permanently discontinue	Permanently discontinue
Hypothyroidism		Therapy with pembrolizumab can be continued while thyroid replacement therapy is instituted	Therapy with pembrolizumab can be continued while thyroid replacement therapy is instituted
Infusion Reaction	2 ^b	Toxicity resolves to Grade 0-1	Permanently discontinue if toxicity develops despite adequate premedication
	3-4	Permanently discontinue	Permanently discontinue

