5.8 Clinical Criteria for Early Trial Termination

Early trial termination will be the result of the criteria specified below:

1. Quality or quantity of data recording is inaccurate or incomplete
2. Poor adherence to protocol and regulatory requirements
3. Incidence or severity of adverse drug reaction in this or other studies indicates a potential health hazard to subjects

Stopping Rules:

The number of patients (15) planned for this study is not sufficient to represent the population as a whole nor is it sufficient to complete a powerful statistical analysis.

The first 3 subjects will be treated at 100 mg every 3 weeks for 6 cycles. If one subject of the three subjects requires the dose of MK-3475 be withheld or discontinued, the 100 mg cohort will be expanded to 6 subjects. If two out of three or two out of six subjects

develop toxicity that requires the dose to be withheld or discontinued, the dose will be not be escalated to 200 mg MK-3475 every 3 weeks. All remaining subjects will be treated at 100 mg MK-3475 every 3 weeks for 6 cycles.

For study subject safety, if there is any fatal toxicity or morbidity event related to the study treatment or procedures, or if one or more of the 15 subjects treated experience a grade 4 toxicity, then subject accrual will be suspended and all data pertaining to the events will be reviewed by the Study Investigators and Data Safety Review Team to determine if there is the need for any corrective actions.

Once that review is completed and any appropriate action is taken, subject accrual will begin again, if the Data Safety Review Team members have approved continuation of the study. If there is a second fatal treatment/morbidity event related to the study treatment or procedures, the study will be terminated. If 4 of 15 subjects experience grade 4 toxicities, the accrual will be suspended and reviewed for added appropriate measures. If 5 subjects experience grade 4 toxicity, the study will be terminated.

Non-local safety reports will be evaluated as they are received. Tabulations of the reports will be provided to the Data Safety Review Team with access to the full reports for completeness of review.

4. Plans to modify or discontinue the development of the study drug

In the event the investigational product is no longer available, ample notification will be provided so appropriate adjustments to subject treatment can be made.

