6.0 DATA SAFETY REVIEW TEAM

6.1 Data/Efficacy Review

A Data Safety Review Team will be formed to evaluate the safety of the combination of the treatments as well as to objectively comment on any apparent decreased efficacy. The first three subjects will be treated at 100 mg rather than the full 200 mg every 3 weeks. Once the first three subjects have completed therapy and no adverse events have called for an earlier meeting, the Data Safety Review Team will meet to discuss the escalation of the dose to 200 mg. If one subject of the three subjects requires the dose of MK-3475 be withheld or discontinued, the 100 mg cohort will be expanded to 6 subjects. If two out of three or two out of six subjects develop toxicity that requires the dose to be withheld or discontinued, the dose will not be escalated to 200 mg MK-3475 every 3 weeks. All remaining subjects will be treated at 100 mg MK-3475 every 3 weeks for 6 cycles.

The Data Safety Review Team will again evaluate the patient safety and efficacy response after 7 and 10 subjects have completed the treatment regimen. The committee will also be charged with enforcing the stopping rules. All adverse event data, as well as patient response to treatment, will be presented to the committee and the committee will be allowed to

Product: MK-3475

Protocol/Amendment No.: Amendment 5, 21 October 2019

deliberate in a closed session to advise on the continued enrollment of subjects and to propose any protocol amendments to enhance the study.

Remainder of Page Intentionally Left Blank

Product: MK-3475

Protocol/Amendment No.: Amendment 5, 21 October 2019

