8.1.6.2 Treatment Period

8.1.6.2.1 Dose Escalation

The first 3 enrolled patients will be treated with 100 mg of MK-3475 every 3 weeks for 6 cycles. If one subject of the three requires the dose of MK-3475 to be withheld or discontinued, the 100 mg cohort will be expanded to 6 subjects. If two out of three or two out of six subjects develop toxicity that requires the dose to be withheld or discontinued, the dose will not be escalated to 200 mg MK-3475 every 3 weeks. All remaining subjects will be treated at 100 mg MK-3475 every 3 weeks for 6 cycles.

Physical examination and assessment of toxicity will be performed before each administration of MK-3475. A CBC will be obtained on Day 1 of every 3-week cycle. Biochemistry panel examining electrolytes, and liver enzymes will be performed on Day 1, Cycle 1 of MK-3475, at Weeks 7, 10 and 13, and at the end of therapy (Week 19). Treatment will not proceed unless laboratory values are acceptable. Urinalysis will occur at weeks 7-12 prior to each BCG treatment. BCG treatment will not proceed unless urinalysis results are acceptable. Collect and record non-serious and serious adverse events and assignment of toxicity grade (NCI CTCAE, Version 4) at each visit. Collect and record any changes in concomitant medication.

Product: MK-3475

Protocol/Amendment No.: Amendment 5, 21 October 2019

Subjects will be provided with an oral thermometer and a diary (Appendix H) to document twice daily oral temperatures. The diary will also ask for documentation of other symptoms to help monitor for systemic infection of BCG.

The AUA IPSS and QOL questionnaires are to be administered at Day 1 Cycle 1 and Week 10 visit prior to any study procedures.

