8.1.6.5 Treatment Discontinuation/Safety Follow-Up Visit

The Treatment Discontinuation Visit and Safety Follow-Up Visit include identical procedures and assessments. Subjects withdrawn from treatment prior to completion of the Treatment Period should undergo a Discontinuation Visit for safety purposes and may occur any time within 30 days of the subject discontinuing treatment, but preferably prior to the subject initiating a new treatment. The mandatory Safety Follow-Up Visit should be conducted approximately 30 days after the last dose of trial treatment or before the initiation of a new anti-cancer treatment, whichever comes first. All AEs that occur prior to the Safety Follow-Up Visit should be recorded. Subjects with an AE of Grade >1 will be followed until the resolution of the AE to Grade 0-1 or until the beginning of a new anti-neoplastic therapy,

Product: MK-3475

Protocol/Amendment No.: Amendment 5, 21 October 2019

whichever occurs first. SAEs that occur within 30 days of the end of treatment or before initiation of a new anti-cancer treatment should also be followed and recorded.

Assessments at the Discontinuation/Safety Follow-Up Visit include a full physical examination, ECOG Performance Status and vital signs. Laboratory assessments include hematology, chemistry, and urinalysis, as well as evaluation of thyroid function. Concomitant medications and toxicity assessment will be recorded as well.

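### The 100 mg escalation count is worded as a dosing action, so Table 3-grade toxicity first seen after dose 6 falls outside the mandatory bar

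*Combined protocol and SAP*

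**What the plan says.** Section 5.2.3.1 starts the first three subjects at 100 mg and sets two numeric steps. If one of the three needs MK-3475 held or stopped, the cohort grows to six. The bar to 200 mg is: "If two out of three or two out of six subjects develops toxicity that requires the dose to be withheld or discontinued", everyone still to be treated stays at 100 mg. Sections 5.8, 6.1 and 8.1.6.2.1 repeat the rule with the same event. None of the four attaches a dose-limiting toxicity definition, a grade or an observation window.

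Section 5.2.3.3 introduces the hold and discontinue grades of Table 3. Of adverse events linked to pembrolizumab it says: "These adverse events may occur shortly after the first dose or several months after the last dose of treatment".

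The flow chart (Section 7.1) gives MK-3475 at Weeks 1, 4, 7, 10, 13 and 16. After Day 1, Section 8.1.6.2.1 places the biochemistry panel "at Weeks 7, 10 and 13, and at the end of therapy (Week 19"; the flow chart agrees. Chemistry is taken again at Safety Follow-Up, about 30 days after the last dose, where Section 8.1.6.5 says: "Laboratory assessments include hematology, chemistry, and urinalysis, as well as evaluation of thyroid function".

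Section 5.2.3.1 has the Team meet when three subjects have been enrolled and treated. Section 6.1 sets the meeting as follows: "Once the first three subjects have completed therapy and no adverse events have called for an earlier meeting". Neither makes it wait for Safety Follow-Up.

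Other controls sit beside the count. Table 2, footnote a: "If the Data Safety Review Team approves, the dose will be escalated to 200 mg with the fourth subject enrolled". Section 4.2.2: "If the first 3 patients do not have any significant safety or efficacy issues the dose will be escalated to 200 mg". Section 5.8 suspends accrual "if there is any fatal toxicity or morbidity event related to the study treatment or procedures", or if any subject has a grade 4 toxicity.

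**The concern.** The numeric count is the only part of the escalation rule that makes expansion, or staying at 100 mg, compulsory. An event defined as a dose being withheld or stopped can occur only while a dose is still due. The same toxicity, at the same grade and with the same relation to the drug, therefore counts at Week 13 and not at Week 19. The protocol itself expects some events after the last dose.

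The events left out are not trivial. Five Table 3 rows that can start late act from grade 2: colitis, liver, hypophysitis, pneumonitis and nephritis. For all five, Section 5.4.1 calls for corticosteroids at grade 2, with a taper of at least four weeks. A 100 mg cohort with one or two such subjects need not expand or stop. The step to 200 mg then rests on the Team's judgement and on a condition about significant safety issues that is not defined.

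**Working it through.** The plan states no target toxicity rate and no operating characteristics for this rule, so there is no figure to reproduce. The check is of the wording against the schedule.

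**1. Nominal days since Day 1** (flow chart; week w falls 7 × (w − 1) days after Day 1):
- Week 13: 7 × 12 = 84
- Week 16, dose 6: 7 × 15 = 105
- Week 19: 7 × 18 = 126
- Safety Follow-Up: 105 + 30 = 135

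**2. Chemistry around the last dose.** The scheduled draws fall on days 84 and 126, which are 42 days apart. Dose 6 is given on day 105, between them. A silent liver, renal or glucose abnormality that starts after the day 84 draw is first seen on schedule on day 126, 21 days after the last dose. So chemistry abnormalities starting in the last 135 − 84 = 51 of 135 days (38%) are seen on schedule only when no dose is left. For toxicity noticed clinically as it starts, the figure is 135 − 105 = 30 of 135 days (22%). These are shares of the calendar, not of toxicity. Unscheduled tests (Section 8.1) could find some abnormalities sooner.

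**3. One event, two dates.** Take a drug-related grade 2 ALT rise, which Table 3 says must lead to a hold.
- Seen on the Week 13 draw: doses 5 and 6 are due, MK-3475 is held, and the subject counts.
- Seen on the Week 19 draw: no dose is due, nothing is held or stopped, and the subject does not count.

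**4. What that does to a cohort of three** (hypothetical cases, with no other events):

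| Subjects with this rise first seen at Week 19 | Count as worded | Count if late events were included | Step required if included |
|---|---|---|---|
| 1 | 0 of 3 | 1 of 3 | Expand to 6 |
| 2 | 0 of 3 | 2 of 3 | No escalation |

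As worded, neither cohort meets a mandatory step.

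**5. What the other numeric rules catch.** The Section 5.8 suspension does not depend on dosing, so late grade 4 and related fatal events are covered. Its morbidity term is undefined and may take in late grade 3. Grade 2 lies below the grade 4 trigger. The residue is therefore mainly grade 2-3, and perhaps mostly grade 2.

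**6. Meeting date.** Section 8.1.6.2.1 puts the end of therapy at Week 19. A meeting then would precede the last cohort subject's Safety Follow-Up by 135 − 126 = 9 days. If therapy were taken to end at the last infusion, the interval would be 135 − 105 = 30 days.

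**The case against.** The strongest objection is textual. Section 5.2.3.3 says when MK-3475 must be withheld, by pointing to Table 3. Read together with Section 5.2.3.1, a toxicity that requires withholding could mean one that reaches a Table 3 grade, with or without a dose left. That is a plausible reading, but no section states it. The expansion trigger, which speaks of a subject needing the MK-3475 dose held or stopped, fits it poorly. If it is what was meant, the proposed clause only makes it explicit.

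The second objection is that the count is a floor. The Team decides on escalation, sees all adverse event data, may wait or decline, and reviews safety again after 7 and 10 subjects. This stands, and it limits the point. A reader might infer that late toxicity is hidden from the decision-maker or that escalation would go ahead regardless; the documents do not support either. What discretion does not do is restore the compulsory expansion or the compulsory bar.

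Third, the timing issue is small. With therapy ending at Week 19, the Team would already have 21 days of data after dose 6. That is conceded. The counting gap, by contrast, applies to every subject in the cohort.

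Fourth, the protocol reports no dose-limiting toxicity with pembrolizumab alone at 1 to 10 mg/kg, and the count already spans all six BCG instillations. Where to end the window is a design choice. This lowers the stakes, but the 100 mg step exists to test the combination, and the present window ends through the wording rather than by a stated decision.

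Fifth, Appendix F (Objective 3) describes 200 mg dosing and samples already collected, so the escalation decision may be past. That changes the form of the remedy, not the reading of the rule.

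**Conclusion.** The point holds as a gap in the numeric bar. On the plain wording of all four statements, drug-related toxicity at a Table 3 hold or discontinue grade that first appears after Week 16 triggers neither expansion to six nor the bar to 200 mg. The missing Week 16 chemistry makes this concrete for liver, renal and glucose abnormalities. It is worth correcting because the correction is cheap, but it is not a failure of oversight.

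The effect size is unknown. Any change in the chance of meeting the bar would have to be built on an assumed toxicity rate and an assumed share of late onset, and the documents give neither. The day counts above describe the schedule only.

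A reader might also infer from the sparse thyroid sampling in the flow chart that thyroid toxicity is a main route through the gap. The documents do not support this. Section 5.4.1 asks for thyroid monitoring periodically during treatment and as clinically indicated. Hypothyroidism never triggers a Table 3 hold, and hyperthyroidism does so only at grade 3-4.

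The conclusion rests on the literal reading of the count and on nominal visit days.

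**What to change.** In Sections 5.2.3.1, 5.8, 6.1 and 8.1.6.2.1, keep the present trigger, so that discretionary grade 2 holds (Table 3, footnote c) and withdrawals forced by Section 5.2.4 still count. Add: *or any drug-related toxicity meeting a Table 3 hold or discontinue threshold, whether or not a dose is still due, through the 30-day Safety Follow-Up Visit*. Apply the addition to both the expansion trigger and the bar. Hold the escalation meeting once the last cohort subject's Safety Follow-Up data are available. Table 3 itself does not change.

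If escalation has already been decided, rescore the 100 mg subjects on this definition from the adverse event data already collected, and give the result to the Team's next scheduled review. If the new count would have required expansion or no escalation, the Team should record whether remaining subjects stay at 200 mg.

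The cost is one clause in four places, using thresholds, a visit and a 30-day recording window that the protocol already has. The meeting, and with it the dose decision for the next subject, moves by about 9 days from Week 19. Cohorts will expand or stay at 100 mg slightly more often. Non-serious events beyond 30 days remain outside the count; later serious events still reach the sponsor under the 90-day reporting rule in Section 9.1.3.1, which shortens to 30 days if new anticancer therapy starts.
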